3.3 Study Variables

3.3.1 Safety Variables

- Adverse events including SAEs and suspected adverse drug reactions (ADRs)
- Clinical laboratory values including inhibitor (immunogenicity) and functional activity testing
- Thrombogenicity assessment
- Vital signs
- Physical examination

3.3.2 Efficacy Variables

- Bleeding duration
- Bleeding severity
- Investigator's qualitative assessment of hemostasis utilizing a 4-point rating scale (evaluated as "excellent," "good," "poor," or "no response" in response to therapy with Fanhdi received by the subject in a hospital or another location under the investigator's direct supervision [[Table 3-1](#)]).
- Amount of Fanhdi (IU/kg) used per subject and per year
- Amount of Fanhdi (IU/kg) used per infusion
- Use of other hemoderivatives per bleeding episode
- Overall clinical efficacy

3.4 Methods and Timing for Recording Study Parameters

In this clinical study, subjects will receive the most suitable dose of Fanhdi, according to the investigator's discretion, to achieve satisfactory hemostasis. There will be no intervention with the prescribing habits or practices of the investigator's standard medical care; however, the investigator is expected to treat the subject within the approved labeling for dose and frequency of Fanhdi (see [Section 3.1.1](#)).

Subjects will be followed for 12 months after the first infusion of Fanhdi, in which information gathered from any episode (spontaneous or traumatic bleeding), surgery or invasive procedure, and the response to treatment and consumption of Fanhdi will be collected.

An assessment of the overall clinical efficacy of Fanhdi throughout the study will be performed and collected by the investigator utilizing a 4-point rating scale (evaluated as "excellent," "good," "poor," or "no response" in response to therapy with Fanhdi received by the subject in a hospital or another location under the investigator's direct supervision). Clinical efficacy assessment ratings are described in Table 3-1 ([25](#)).

Table 3-1 Assessment of Clinical Efficacy

Rating	Clinical Efficacy	
Excellent	Hemostasis comparable with that expected for individuals without known bleeding disorders	No increase in FVIII/VWF dosing required
Good	Hemostasis slightly inferior to that expected for individuals without known bleeding disorders	Minor increase in FVIII/VWF dosing required
Poor	Reduced hemostasis is compared with that expected for individuals without known bleeding disorders	Significant increase in FVIII/VWF dosing required; no need for alternative therapy
No Response	Severe bleeding despite FVIII/VWF therapy	Significant increase in FVIII/VWF dosing required and/or need for alternative therapy to control bleeding

3.5 Study Data Collection

The medical records of all subjects meeting the study eligibility requirements will be reviewed. Safety ([Section 3.5.1](#)) and efficacy ([Section 3.5.2](#)) information will be collected from each subject record (as performed at the discretion of the investigator per standard of care).

3.5.1 Safety Assessments

3.5.1.1 Adverse Events

Adverse events (including suspected ADRs) occurring at any time between signing of the subject's informed consent form (ICF) and the last day of the subject's participation in the clinical study will be recorded in the appropriate eCRF and in the subject's source documents.

Local infusion-site reactions where the symptoms/signs lead to infusion interruption or discontinuation, require concomitant medication, or have an impact on the general condition of the subject as judged by the investigator, will be collected and documented as AEs.

Adverse events will be elicited by spontaneous reporting by the study individual or by a non-leading inquiry or direct observation by the study staff according to the investigator's standard of care.

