4.3 Adverse Event Definitions

4.3.1 Adverse Events

An AE is defined as any untoward medical occurrence in a subject or clinical investigation subject administered a medicinal product or study treatment and which does not necessarily have a causal relationship with this administration. An AE can therefore be any unfavorable and unintended sign (including any abnormal laboratory finding, for example), symptom, or disease temporally associated with the use of a medicinal product, whether or not considered related to the medicinal product.

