4.3.2 Suspected Adverse Drug Reactions

All noxious and unintended responses to a medicinal product or study treatment related to any dose should be considered suspected ADRs. The phrase “responses to a medicinal product” means that a causal relationship between a medicinal product or study treatment and an AE is at least a reasonable possibility.

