4.5 Severity of Adverse Event or Suspected Adverse Drug Reaction

Adverse events and suspected ADRs will be classified depending on their severity according to the following definitions:

Mild: an AE which is well tolerated by the subject, causing minimum degree of malaise and without affecting normal activities.

Moderate: an AE that interferes with the subject's normal activities.

Severe: an AE that prevents the subject from performing their normal activities.

Adverse event and suspected ADR severity gradation must be distinguished from an AE and suspected ADR seriousness gradation, which is defined according to event consequence. For example, headache can be mild, moderate or severe but not necessarily serious in all these cases.

The investigator will be responsible for assessing the AE and suspected ADR intensity during the clinical study, taking into account current criteria included in this section.

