5.3.1 Adverse Events

Safety analysis will be primarily focused on a descriptive analysis of suspected ADRs. Safety assessment will be based on the prevalence of suspected ADRs that occurred during the clinical study.

Adverse events will be coded and classified using MedDRA terms (system organ class [SOC] and preferred term [PT]).

Adverse events will be classified as treatment-emergent AEs (TEAEs) or non-treatment-emergent AEs (non-TEAEs) depending on the comparison of AE onset date/time with the start date/time of study treatment after the subject joins the study. A TEAE will be defined as an AE which occurs between the beginning of the first infusion of study treatment after the subject joins the study and the final visit of the clinical study. A non-TEAE will be defined as an AE which occurs prior to the start of study treatment after the subject joins the study. Non-TEAEs and TEAEs will be summarized separately.

All AEs will be summarized by presenting subject incidences and percentages, and they will also be listed by subject and by SOC.

In addition, TEAEs, including suspected ADRs, will be summarized by SOC, PT, causal-relationship, intensity (severity) and seriousness (serious vs non-serious) using descriptive statistics. Each subject will only be counted once at each level of SOC or PT. For the summary by severity or causality, a subject will only be counted once per SOC or PT using the most severe AE or the AE with the strongest causal relationship to study treatment.

Adverse events temporally associated to the infusion of study treatment (ie, infusional AEs, including infusional suspected ADRs), will be summarized by presenting infusion/subject incidences and percentage and ordered by ordinal number of infusions, and listed. Temporally associated AEs occurring during study drug infusion or within 24 hours post the end of study drug infusion, and occurring during or within 72 hours post the end of study drug infusion will be summarized separately.

Subjects with a SAE or who withdraw from the study because of an AE will also be individually listed and summarized.

5.3.2 Clinical Laboratory Values Including Inhibitor (Immunogenicity) and Functional Activity Testing

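### The rule for local infusion-site reactions in Protocol Section 3.5.1.1 reads as a consequence threshold that Sections 4.3.1, 4.3.2 and 4.8 do not have, so some suspected ADRs may go unrecorded

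*Protocol*

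**What the plan says.** Section 3.5.1.1 opens with a general rule that has no threshold: "Adverse events (including suspected ADRs) occurring at any time between signing of the subject's informed consent form (ICF"). Recording runs until participation ends. Its next paragraph deals with one class of event: "Local infusion-site reactions where the symptoms/signs lead to infusion interruption or discontinuation, require concomitant medication, or have an impact on the general condition". The last of these conditions is left to the investigator's judgement, and a reaction meeting any of the three is entered as an AE. Nothing is said about local reactions that meet none of the three conditions.

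The definitions are wider. Section 4.3.1: "An AE can therefore be any unfavorable and unintended sign (including any abnormal laboratory finding, for example), symptom, or disease temporally associated". The link meant there is to use of the product. Section 4.3.2: "All noxious and unintended responses to a medicinal product or study treatment related to any dose should be considered suspected ADRs", with the qualification that a causal relationship must be at least a reasonable possibility. Section 4.5 has a mild grade: "an AE which is well tolerated by the subject, causing minimum degree of malaise and without affecting normal activities". Section 4.8 makes the investigator responsible for recording all AEs, serious or not.

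On the analysis, Section 5.3.1 states: "Safety analysis will be primarily focused on a descriptive analysis of suspected ADRs". It bases the safety assessment on the prevalence of these reactions. It also asks for infusional AEs and infusional suspected ADRs by infusion and by subject, in 24-hour and 72-hour windows.

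**The concern.** The two sets of rules treat the same event differently. Take a brief painful or red infusion site that needs no medication, does not stop the infusion and leaves the subject otherwise well. Under Section 4.3.1 it is an AE. If the product is a reasonable possible cause, it is a suspected ADR under Section 4.3.2, gradable as mild under Section 4.5. Under Section 3.5.1.1 it meets none of the stated conditions. The protocol does not say which rule prevails.

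The main safety result is at stake. Suspected-ADR prevalence and the infusional summaries are built from what centers enter. Section 3.3.1 lists no separate local-tolerability variable, so a reaction not entered as an AE has no other named place in the data. This is a collection rule, so an analysis plan written later cannot recover the events. In a multi-center study of about 15 subjects, a difference in how centers read one sentence could also be mistaken for a difference in tolerability.

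**Working it through.** The protocol has no calculated figure to reproduce: Section 5.5 says the sample size was not formally calculated, and no local-reaction rate is given. The check is a comparison of the texts, followed by an illustration.

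**1. The event described above, under each rule**

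| Protocol section | Threshold | Result for this event |
|---|---|---|
| 3.5.1.1, general rule | none | recorded |
| 3.5.1.1, local reactions | interruption or discontinuation, medication, or general effect | not among those listed |
| 4.3.1 | none | AE |
| 4.3.2 | reasonable possibility of causality | suspected ADR if that is judged to be met |
| 4.5 | none | mild |
| 4.8 | none | must be recorded |

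**2. Is the local-reaction sentence a threshold?** If every local reaction were recorded anyway, the sentence would add nothing. The protocol uses similar wording as a filter elsewhere: abnormal vital signs (3.5.1.4), physical findings (3.5.1.5) and laboratory results (5.3.2) become AEs when judged clinically significant. A center would reasonably read this sentence in the same way. That remains an inference, because no exclusion is written.

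**3. Direction.** Not recording a reaction cannot add a subject or an infusion to the ADR count. It removes a subject only if that subject has no other recorded ADR, and it removes an infusion from an infusional ADR count only if no other such reaction was recorded for it. The denominators do not change, so prevalence and the infusional percentages stay the same or fall.

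**4. Unit of effect.** With n = 15 (Section 5.5, approximate), one missed subject is worth 1/15 = 6.7 percentage points. For scale, the exact 95% upper limit for 0/15 is 1 − 0.025^(1/15) = 21.8%.

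**5. Illustration with assumed rates.** Let q be the share of subjects with a local reaction and f the fraction of those whose reactions all stay below the threshold. Neither is in the protocol.

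- Expected subjects affected = 15q. Expected subjects recorded = 15q(1 − f).
- Chance that at least one is recorded = 1 − [1 − q(1 − f)]^15.
- At q = 0.20 and f = 0.75, 15 × 0.20 = 3.0 subjects are affected and 15 × 0.05 = 0.75 are recorded. The chance of seeing at least one is 1 − 0.80^15 = 96.5% with full recording and 1 − 0.95^15 = 53.7% with the threshold.
- For q from 0.05 to 0.30 and f from 0.25 to 0.90, affected subjects range from 15 × 0.05 = 0.75 to 15 × 0.30 = 4.5. Recorded subjects range from 15 × 0.05 × 0.10 = 0.075 to 15 × 0.30 × 0.75 = 3.4.

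The range is too wide to serve as an estimate. It shows only that the effect could be negligible or could decide whether any local reaction appears in the report.

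**The case against.** The strongest reply is that the sentence includes events and excludes none. It does not say only, the general rule just before it covers all AEs, and Sections 4.3.1, 4.3.2 and 4.8 all require recording. On that reading a careful center records everything and nothing is lost. This stands to the extent that filtering is possible but not fixed. It does not remove the inconsistency: a sentence that would otherwise have no function invites the restrictive reading.

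Other points on that side also stand, and they rule out several stronger conclusions that a reader might draw:

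- *That the mild grade would be emptied, or every mild local reaction lost.* The conditions concern consequence, not severity grade. A mild reaction that needs medication or interrupts the infusion is still collected, and the mild grade covers all other kinds of AE.
- *That every unrecorded local reaction is a lost ADR.* Section 4.3.2 requires a reasonable possibility of causality, and Section 4.4 leaves that to judgement case by case.
- *That thrombosis at the infusion site could be missed.* Sections 3.5.1.3 and 4.3.3 record all thromboembolic events as AEs without condition.
- *That the named safety objective is compromised.* Section 2.1 names immunogenicity and thrombogenicity, and this sentence touches neither.

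It can also be said that clinical-significance screens are usual in this protocol and that data come from routine records, so removing the threshold may recover few events. The comparison with laboratory values is weak, because an out-of-range value need not be untoward, whereas a local reaction is itself an unfavorable sign or symptom. That few events may be recovered is plausible and cannot be tested from the document.

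**Conclusion.** The point holds as an unreconciled inconsistency in a data-collection rule. Section 3.5.1.1, read naturally, sets a consequence threshold for local infusion-site reactions that the AE and ADR definitions and the recording duty do not contain. Where a center applies it, the suspected-ADR prevalence and the 24-hour and 72-hour infusional summaries can only be lowered. Where centers differ, their counts are not comparable.

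A reader might infer that a downward bias of known size is built into the study. The document does not support that: it fixes no uniform filter and gives no local-reaction rate. The only firm figure is the unit of 6.7 percentage points per subject whose sole ADR is missed, assuming 15 subjects in the denominator. The analysis is descriptive with no decision threshold, so the consequence is an incomplete or uneven description of tolerability rather than a wrong test result. The point still deserves correction, because the affected result is the stated main focus of the safety analysis and unrecorded events cannot be recovered later.

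**What to change.** Reconcile Section 3.5.1.1 with Section 4.3. State that every local infusion-site reaction meeting the AE definition in Section 4.3.1 is recorded and graded under Section 4.5. Use the three consequence conditions only in presentation, by showing infusion-site reactions on a separate line, split into those that did and did not meet a condition. Put the same instruction in the eCRF guidance so that all centers follow it.

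If the sponsor prefers to keep the restriction, it should be written as an explicit exclusion that overrides Sections 4.3.1, 4.3.2 and 4.8 for these events. The ADR prevalence and infusional tables should then be labelled as excluding local reactions below the threshold.

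The cost of the first option is one sentence in the protocol, a line of eCRF guidance, a few more AE entries and a possibly slightly higher reported ADR incidence. The second option costs about as little to write, but it leaves the data without those reactions.

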3.5.1.2 Clinical Laboratory Values Including Inhibitor (Immunogenicity) Testing

Clinical laboratory data will be collected at the discretion of the investigator per standard of care. The presence and titer of FVIII and VWF inhibitors will be determined throughout the observational period as performed at the discretion of the investigator per standard of care. The clinical relevance of the inhibitors (according to the investigator) and the cumulative incidence as a function of the number of exposures to Fanhdi will be collected. Clinical laboratory data will be recorded in the appropriate eCRF and in the subject's source documents.

3.5.1.3 Thrombogenicity Assessment

Monitoring assessments for the clinical signs and symptoms of thromboembolic events will be conducted at the discretion of the investigator per standard of care and collected.

Monitoring for clinical signs and symptoms of thromboembolic events will be performed in subjects who undergo a surgical or invasive procedure according to the investigator's standard of care will be collected. All thromboembolic events will be recorded in the appropriated eCRF and in the subject's source documents as AEs and reported accordingly.

3.5.1.4 Vital Signs

Vital signs will be measured by a medically certified individual or a nurse according to the standard clinical practice.

The following vital signs (assessed at the discretion of the investigator per standard of care) will be collected:

- Temperature (T)
- Heart rate (HR)
- Respiratory rate (RR)
- Blood pressure (BP [systolic and diastolic BP])

Vital signs will be routinely monitored by the study staff according to standard clinical practice. Vital signs will be recorded in the appropriate eCRF and in the subject's source documents. Vital signs abnormalities judged by the investigator as clinically significant will be collected and documented as AEs.

3.5.1.5 Physical Examination

A medically certified individual will conduct a physical examination according to standard clinical practice. Any physical examination abnormalities judged by the investigator as clinically significant will be considered AEs. Physical examination data will be recorded in the appropriate eCRF and in the subject's source documents.

3.5.2 Efficacy Assessments

3.5.2.1 Bleeding Episodes

Information from any bleeding episode occurring during the observation period, including spontaneous or traumatic bleeding will be collected. The response to treatment and extent of exposure to Fanhdi will be recorded in the eCRF and subject's source documents.

A bleeding episode will be categorized according to International Society on Thrombosis and Haemostasis (ISTH) guidelines (26) as follows:

Major bleeds are defined as bleeding:

- with a fall in hemoglobin of ≥ 2 g/dL, or
- with transfusion of ≥ 2 units of packed red blood cells or whole blood, or
- that occurs in a critical location, ie, intracranial, intraspinal, intraocular, retroperitoneal, intraarticular, or pericardial, or
- that causes death

Clinically relevant non-major bleeds are defined as bleeding:

- that does not meet criteria for major bleeding, and
- that requires any medical or surgical intervention to treat the bleeding

During bleeding episodes, information on the following procedures and assessments (performed at the discretion of the investigator) will be collected:

- The use of any blood derivative (ie, FVIII concentrates, transfusions [plasma, platelets, and red blood cells (RBCs)], cryoprecipitate) or antifibrinolytic agents
- Any complications
- Concomitant medication and AEs
- Clinical evaluation of thrombogenicity

Bleeding severity (mild, moderate, severe) will be based on investigator's assessment. In the instance of a severe bleeding episode, information on any measures of the following (assessed at the discretion of the investigator per standard of care) will be collected:

- Vital signs (T, HR, RR, BP)
- Blood samples for any of the following:
 - Clinical laboratory assessment of renal (creatinine, blood urea nitrogen [BUN]), hepatic (alanine aminotransferase [ALT], aspartate aminotransferase [AST], alkaline phosphatase [ALP], and total bilirubin [TB]), and/or hematological parameters (including hemoglobin, hematocrit, platelets, RBC count including RBC morphology, white blood cell [WBC] count with differential, and absolute reticulocyte count [ARC])
 - Factor VIII and VWF functional activity

Information on the overall evaluation of the bleeding episode according to the investigator, including the duration and severity of the bleed, clinical correction of hemostasis, and overall clinical efficacy will be collected.

Clinical Efficacy in Bleeding Episodes

To determine the clinical efficacy of Fanhdi for bleeding episodes in subjects with VWD, information will be collected on the nature, location, duration (time to hemostasis of the bleed between the start of the first Fanhdi infusion and the cessation of bleeding) and severity of the bleeding episodes as assessed by the investigator.

In addition, the number of infusions and the total amount of Fanhdi dosed for bleeding episodes and the use of additional blood derivatives (ie, FVIII concentrates, transfusions [plasma, platelets, and RBCs], cryoprecipitate) or antifibrinolytic agents will be collected. Efficacy data will be recorded in the appropriate eCRF and in the subject's source documents.

Information on the clinical correction of hemostasis and overall clinical efficacy of bleeding episodes as assessed by the investigator utilizing a 4-point rating scale ("excellent," "good," "poor," or "no response" [Table 3-1, 25]) will be collected over the course of 12 months of therapy.

3.5.2.2 Surgical or Invasive Procedures

The definitions of surgical procedures (classified into 2 categories [major or minor]) and invasive procedures are provided in Table 3-2 (25). Information from all surgical or invasive procedures occurring during the observation period will be collected and the response to treatment and extent of exposure to Fanhdi will be recorded in the appropriate eCRF and in the subject's source documents.

Table 3-2 Definition of Surgical and Invasive Procedures

Major surgery	Usually involves the use of regional or general anesthesia and penetrates and exposes one of the major body cavities (eg, skull, chest, neck, abdomen) or one of the major joints (eg, shoulder, hip, spine) or stresses vital organs
Minor surgery ^a	Any surgery or procedure not considered major
Invasive procedure ^a	Any procedure that avoids the use of cutting open surgery in favor of closed surgery; such procedures involve the use of instruments with indirect observation of the surgical field through an endoscope or similar device with reduced associated trauma

^a Data for minor and invasive procedures are combined except for dose and duration of therapy

During a surgery or invasive procedure, information on the following procedures and assessments (performed at the discretion of the investigator per standard of care) will be collected:

- The use of any blood derivative (ie, FVIII concentrates, transfusions [plasma, platelets, and RBCs], cryoprecipitate) or antifibrinolytic agents
- Any complications
- Concomitant medication and AEs during the surgical or invasive procedures
- Clinical evaluation of thrombogenicity

Information on the following measures (assessed at the discretion of the investigator per standard of care) will be collected:

- Vital signs (T, HR, RR, BP)
- Blood samples for any of the following:
 - Clinical laboratory assessment of renal (creatinine, BUN), hepatic (ALT, AST, ALP, and TB), and/or hematological parameters (including hemoglobin, hematocrit, platelets, RBC count including RBC morphology, WBC count with differential, and ARC)
 - Factor VIII and VWF functional activity

During the post-operative period, the administration of Fanhdi will continue per the investigator's standard medical practice.

Clinical Efficacy in Surgery or Invasive Procedure

To determine the clinical efficacy of Fanhdi for surgical or invasive procedures in subjects with VWD, information will be collected on the duration of bleeding (measured from the start of Fanhdi administration through the time to hemostasis) and severity of bleeding (defined in [Section 3.5.2.1](#)) as assessed by the investigator.

In addition, the number of infusions, total amount of Fanhdi dosed (at the time of the surgical or invasive intervention and immediately thereafter), and the use of additional blood

derivatives (ie, FVIII concentrates, transfusions [plasma, platelets, and RBCs], cryoprecipitate) or antifibrinolytic agents will be collected. Efficacy data will be recorded in the appropriate eCRF and in the subject's source documents

Clinical correction of hemostasis and overall clinical efficacy in surgery or invasive procedure, as assessed by the investigator utilizing a 4-point rating scale ("excellent," "good," "poor," or "no response" [Table 3-1, 25]) will be collected.

